This information will be inputted into NEPTUNE-Link and will be automatically transferred to the SMS system. Participant responses to text messages will be returned to NEPTUNE-Link for the local study team to review.

Participants will receive text messages asking about home urine protein monitoring results, relapse triggers (infections, allergies, stressors), edema status and location, consumption of prescribed immunosuppressive medications and nephrotic syndrome related absences from school/work. Parent or child (≥ 12 yrs) can respond to text messages at the discretion of the parent/child dyad (with approval from coordinator/local PI). The SMS alert system may be paused for planned vacations or during hospitalizations by the site study coordinator. SMS pause start and end dates will be entered into the NEPTUNE-Link SMS administration CRF to implement the pause.

Alerts will be sent to the email addresses designated in NEPTUNE-Link for items such as dipstick $\leq 2+$ for 3 days after being trace/negative, abdominal or genital edema, anasarca, if the patient reports not taking immunosuppressive medications, or if there is no response for one week without prior notification to the study team to “pause” the system.

3.E. Study Data

Extensive data will be collected during the NEPTUNE cohort studies. These data descriptions are provided in the following six sections:

- 1) Primary Outcome Variables
- 2) Secondary Outcome Variables
- 3) Intra-renal Gene Expression Exposure Variables
- 4) Histopathology Variables
- 5) Overview Biochemical Measures
- 6) Other Exploratory Exposure and Intermediate Outcome Variables

3.E.1. Primary Outcome variables

The two primary outcome variables are:

- (1) Event rate of change in urinary proteinuria excretion (defined as remission, partial remission and non-remission); and
- (2) Rate of change in renal function defined as:
 - (a) 25 mls/min/1.73m² reduction in follow-up estimated GFR (using the 4-variable MDRD equation for ages ≥ 18 years and modified Schwartz for ages < 18 years) compared to baseline estimated GFR
 - (b) 50% decline in follow-up estimated GFR compared to baseline measurement
 - (c) End stage renal disease defined as estimated GFR ≤ 10 cc/min, initiation of maintenance dialysis or preemptive kidney transplantation).

3.E.1.a. Proteinuria

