Proteinuria (U:C) After Observation Period	Standard Definition	Definitions for the Cohorts
$U:C \leq 0.3g$	Complete Remission (CR)	Complete/Partial Remission
Reduction in U:C of $>50\%$ plus final $P:C \leq 3.5g$ but $>0.3g$	Partial Remission (PR)	
Reduction in U:C of $>50\%$ with final $P:C > 3.5g$	Limited Response (LR)	No Response
Reduction in U:C of $<50\%$. (include increase in U:C $<50\%$)	Non-Response (NR)	
Proteinuria increases by $>50\%$	Progressive Proteinuria (PP)	
New development of nephrotic range proteinuria, i.e., >3.5 P:C after reaching a complete or partial remission	Relapse	Relapse

3.E.1.b. Renal Function

The main renal function measures in the cohort studies include serum creatinine, serum Cystatin C, a 24-hour urinary clearance of creatinine, and estimated GFR using the MDRD equation for adults and modified Schwartz formula for continent children under 18 years. Serum Cystatin C assay will be deferred until funds for ancillary studies become available. The schedule of these measures is summarized in Table 4.

Table 4. Schedule of Renal Function Measurements in the NEPTUNE main cohorts

Measure	Collection Schedule
Serum creatinine	Every visit
24-hour urinary creatinine excretion	Every visit
Estimated GFR	Every visit
Serum Cystatin C	Every visit*

* Funds pending

3.E.1.b.(a) Creatinine-based Measures

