In clinical practice and large-scale epidemiological research projects the serum creatinine, estimated GFR and timed urinary creatinine clearance have been used for diagnosis and monitoring the progression of renal disease (90-92). These three measures will be ascertained in the current study visit. Factors other than GFR—including generation, tubular secretion, and extrarenal elimination of creatinine—affect serum creatinine concentration. Therefore, use of these serum creatinine or creatinine clearance determinations may not always provide an accurate estimate of renal function (92,93). The most widely utilized estimating equation (4-variable MDRD) may not be sensitive enough to detect progression of renal disease during the time frame of the study. The NEPTUNE will use the three measures of renal function (serum creatinine, estimated GFR and timed urinary creatinine clearance) in an attempt to compensate for the inherent limitations of each single measurement by itself. Ideally, the more precisely measured GFR would be employed but the expense, logistics and participant burden are prohibitive in the current study. The timed urinary creatinine clearance will be performed on a 24-hour urine collection. Because of the significant inconvenience to the participants in collecting a 24-hour urine sample, only six 24-hr urine collections are mandatory and these must include the Baseline Visit [V2], at least one annual follow-up visit [V6, V8, V10, V13] and the final follow-up visit ([V13]) depending on the time of enrollment into the study. Where urinary incontinence prohibits a full 24 hour urine collection, a best alternative urine specimen is to be collected as either a maximum timed urine collection (e.g. 6 to 12 hours), first morning urine collection or random urine collection.

3.E.1.b.(b) Cystatin C

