missed data points, in part because the participation time is not appropriately weighted. For these reasons, time to ESRD provides a secondary outcome that obviates most of the problems inherent in a slope-based analysis. Time to ESRD or 50% decline in baseline GFR or 25 ml/min/1.73m² decline in baseline GFR is particularly attractive as a secondary outcome for the FSGS/MCD study because, in general, time to a specified event constitutes a clearer outcome than a slope. In addition, time to event analysis does not force a functional form (i.e. linear decline) on the process of progression. It is likely that the analytic problems associated with a particular measurement technique are minimized when comparing values for an individual over time. Censoring methods are readily applicable to participants who depart early. Lastly, time to ESRD (i.e. initiation of renal replacement therapy for usual clinical indications) is the most important clinical and economic consequence of FSGS/MCD and MN. This time can be ascertained for participants even after formal completion of the proposed study.

3.E.2. Secondary Outcome Variables

Composite of the following events will be considered as secondary outcomes of the NEPTUNE main cohort study. Additional CRFs or appropriate source documentation may be required for further clarification and/or event adjudication for the following ‘secondary outcomes of special interest’:

- (1) Quality of Life: Patient-reported outcome will be assessed using the Patient Reported Outcome Measurement Information System (PROMIS) from ages 8 and above and parent proxy PROMIS measures will be completed for ages 0-10. Overlap in ages 8 to 10 years allows the complete ascertainment of this assessment in children who may find self-reporting difficult due to delayed reading skills.
- (2) New Onset Diabetes: New-onset diabetes is a diagnosis of diabetes as indicated by one or more of the following that was not present at the time of NEPTUNE enrollment.
 - a) Documented diagnosis of diabetes in the medical record
 - b) Casual (non-fasting) blood glucose > 200 mg/dL
 - c) Fasting blood glucose > 126 mg/dL
 - d) 2 hour glucose > 200 after oral glucose tolerance test
 - e) chronic use (> 6 months) of hypoglycemic therapy outside of pregnancy
 - f) Hemoglobin A1C \geq 6.5% (94)
- (3) Malignancies: Any cancer diagnosis of the skin, hematopoietic system, or solid organ after enrollment in NEPTUNE

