- (4) Infections, Serious and Systemic: Infections including one of the following:
 - a) Documented diagnosis of infection of the skin or subcutaneous tissue (e.g. cellulitis), vascular system, peritoneum, or any vital organ requiring the use of parenteral antibiotics and/or oral antibiotics alone or in combination for a treatment interval of \geq 72 hours.
 - b) Hospitalization for treatment of infection
- (5) Thromboembolic Events: Documented diagnosis of one of the following:
 - a) Embolic cerebrovascular accident
 - b) Deep venous thrombosis
 - c) Renal vein thrombosis or
 - d) Pulmonary embolus
- (6) Hospitalization: Documented hospital admission, including observation for \geq 24 hours.

- (7) Emergency Department/ Observation Unit Visit: Documented visit to an emergency department or observation unit that does not lead to hospitalization and is less than 24 hours.
- (8) Acute Kidney Injury: Documented diagnosis of acute kidney injury as defined by the KDIGO criteria (Kidney Disease: Improving Global Outcomes (KDIGO) Acute Kidney Injury Work Group. KDIGO Clinical Practice Guideline for Acute Kidney Injury. *Kidney inter., Suppl.* 2012; 2: 1–138) and/or renal failure requiring renal replacement therapy <3 months.
- (9) End-Stage Renal Disease (ESRD): Documented chronic dialysis or transplant shall be considered ESRD for the purposes of the NEPTUNE study, a final renal outcome.
- (10) Death:
 - a) Infection-related Death. Documentation of death that is secondary to infection or sepsis.
 - b) Cardiovascular/Cerebrovascular-related Death: Documentation of death from at least one of the following:
 - i) Sudden death
 - ii) Myocardial infarction
 - iii) Congestive heart failure
 - iv) Primary intractable serious arrhythmia
 - v) Peripheral vascular disease
 - vi) Ischemic cerebrovascular accident
 - vii) Hemorrhagic cerebrovascular accident
 - viii) Thromboembolic event (e.g. pulmonary embolus, embolic cerebrovascular accident)
 - c) Malignancy-associated Death: Documentation of death secondary to cancer
 - d) Other Death: Documentation of death that does not fall into the above categories (e.g. primary respiratory failure).

3.E.2.a. Potential Data Sources and Ascertainment Strategy

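### The renal-function outcome changes eGFR equation at age 18 with no rule for participants who cross it, and ESRD is defined differently in 3.E.1 and 3.E.2

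*Protocol*

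**What the plan says.** Section 3.E.1 lists change in renal function as one of two primary outcome variables. Its limbs are:

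- (a) a "25 mls/min/1.73m² reduction in follow-up estimated GFR" from baseline;
- (b) a "50% decline in follow-up estimated GFR compared to baseline measurement";
- (c) "End stage renal disease defined as estimated GFR ≤ 10 cc/min", or maintenance dialysis, or preemptive transplant.

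The equation rule sits inside limb (a): "using the 4-variable MDRD equation for ages ≥ 18 years and modified Schwartz for ages < 18 years". Section 3.E.1.b repeats the split as "estimated GFR using the MDRD equation for adults and modified Schwartz formula for continent children under 18 years", and Table 4 schedules eGFR at every visit.

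The justification in 3.E.1.b.(b) prefers a time-to-event form because "time to a specified event constitutes a clearer outcome than a slope". It adds that the problems of a measurement technique are likely to be smallest when one individual is compared with himself or herself over time.

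On ESRD, 3.E.2(9) says "Documented chronic dialysis or transplant shall be considered ESRD for the purposes of the NEPTUNE study". The end of 3.E.1.b.(b) identifies ESRD with starting renal replacement therapy.

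Cohort A has no lower age limit (3.B.3), and minimum follow-up is 36 months (1.B).

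**The concern.** Limb (a) is a difference between two eGFR values. If they come from different equations, the difference contains a between-equation step as well as any change in kidney function. The age rule is attached to the follow-up value and eGFR is computed at every visit, so the natural reading is that a participant moves from Schwartz to MDRD at the 18th birthday. The within-individual argument in 3.E.1.b.(b) then fails for that participant.

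The study looks for predictors of this outcome. A step that depends on age at entry, sex, height and creatinine can make those variables appear to predict the event, or to protect against it, through measurement alone.

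The ESRD mismatch is a separate defect in the same outcome. A transient eGFR of 10 or below meets 3.E.1(c) but not 3.E.2(9), so the two sections can report different ESRD counts from the same data.

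**Working it through.** The protocol gives no power, error rate or event rate for this three-limb outcome, so there is no figure to reproduce.

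**Who is affected.** Over 36 months, a participant who enters below 18 crosses to the adult equation if aged 15 or more at entry (18 - 3 = 15). The protocol does not say how many such participants are expected.

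**Size of the step.** The coefficients are assumptions.

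- Schwartz = k × height (cm) / creatinine (mg/dL)
- MDRD = C × creatinine^-1.154 × age^-0.203 × (0.742 if female)

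At age 18 and creatinine 0.8, 0.8^-1.154 = 1.294 and 18^-0.203 = 0.556.

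| Assumed set | Participant | Schwartz | MDRD at 18 | Step |
|---|---|---|---|---|
| k 0.413, C 175 | male, 175 cm | 0.413 × 175 / 0.8 = 90 | 175 × 1.294 × 0.556 = 126 | +36 |
| k 0.413, C 175 | female, 163 cm | 84 | 93 | +9 |
| k 0.70, C 186 | male, 175 cm | 153 | 134 | -19 |
| k 0.55, C 186 | female, 163 cm | 112 | 99 | -13 |

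Under the first set the male step is +55 at creatinine 0.6, +25 at 1.0 and +13 at 1.5. The female step is +18 at 0.6 and 0 at 1.5. An assumed race factor of 1.212 raises the creatinine 0.8 steps to +62 and +29. Under the second set the step stays between -17 and -19 for males and between -11 and -13 for females over creatinine 0.6 to 1.5.

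**Effect on limb (a).**

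- First set, male with baseline 90: MDRD must reach 65, which needs a creatinine of about 1.42. On the Schwartz scale that is 51, a like-for-like fall of 39 rather than 25.
- First set, female with baseline 90: the like-for-like fall needed is 28.5.
- Second set, male with baseline 153: the event needs MDRD 128. Solving 186 × 0.556 × creatinine^-1.154 = 128 gives about 0.83. A rise from 0.80 to 0.83 is then enough.

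**ESRD, side by side.**

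| Place | eGFR of 10 or below | Chronic dialysis | Transplant |
|---|---|---|---|
| 3.E.1(c) | counts | counts | counts if preemptive |
| 3.E.2(9) | not listed | counts | counts |
| 3.E.1.b.(b), closing text | not listed | starting renal replacement therapy | starting renal replacement therapy |

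**Secondary check: noise in a first-hit rule.** Take a stable participant with independent error of standard deviation CV × GFR at baseline and at each of seven scheduled visits (months 4, 8, 12, 18, 24, 30 and 36). The chance of a false 25 mL/min fall at one visit is 1 - Φ(25 / (CV × GFR × √2)). At GFR 120 and CV 8% this is 1 - Φ(25 / 13.58) = 3.3%. Chances over seven visits are by simulation with normal errors. The protocol gives no CV, so a range is shown.

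| Baseline GFR | CV 5% | CV 8% | CV 10% |
|---|---|---|---|
| 120, any visit | 0.9% | 14.4% | 26.7% |
| 120, two consecutive visits | 0.05% | 2.6% | 6.7% |
| 60, any visit | 0% | 0.08% | 0.9% |

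Log-normal errors give 13.1% and 23.8% for GFR 120 at CV 8% and 10%. The 50% limb gives essentially no false events at these CVs.

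**The case against.** Several objections have force.

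- **The within-person switch is inferred.** Section 3.E.1 does not say whether age is taken at baseline or at each measurement, and the within-individual argument fits keeping one equation. That narrows the defect to a missing rule. It does not remove it, because the text as written points to age at follow-up.
- **Direction.** A reader might infer that the switch hides real declines in adolescents. The documents do not support that. They name no coefficients, the sign reverses between plausible sets, the effect is small or absent in females with raised creatinine under the first set, and only participants who cross 18 are touched.
- **Confirmation.** A reader might infer that the protocol accepts a single unconfirmed fall. It is only silent, and an analysis plan not shown here could add confirmation or exclude acute episodes. Section 3.E.1.b.(a) concedes that "use of these serum creatinine or creatinine clearance determinations may not always provide an accurate estimate of renal function" and collects three renal measures to compensate, although the event itself uses eGFR alone. The noise figures also depend on an assumed CV and are under 1% at CV 5%. This part is therefore a suggestion only.
- **The absolute threshold.** A fixed 25 mL/min is 21% of 120 and 42% of 60, but 3.E.1.b.(b) argues for absolute change on clinical grounds. It is a reasoned choice and no error.
- **Importance.** Section 3.F.4 calls loss of renal function the second endpoint, 3.E.1.b.(b) calls it secondary in places, and 3.F.5.d uses a different event for cNEPTUNE. Section 3.E.1 nonetheless lists it as primary.

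**Conclusion.** The point holds in two parts. First, the outcome has no equation rule for Cohort A participants who turn 18. Followed as written, those aged 15 to under 18 at entry get an artificial step of unspecified sign and size. In the worked cases at creatinine 0.8 it runs from about -19 to +36 in males and -13 to +9 in females without a race term. The upward step in the 175 cm male reaches or passes 25 mL/min/1.73m² at a creatinine of 1.0 or below. The downward step does not reach 25 by itself but uses up most of it. These sizes rest on assumed coefficients. The missing rule, and its conflict with the protocol's own rationale, do not.

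Second, the ESRD definitions differ, which needs no assumption. How many analysed events either part would change cannot be computed from the protocol. The change should be made, but neither part undermines the study as a whole.

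**What to change.** State in 3.E.1 that baseline and every follow-up eGFR for a participant are computed with the same equation, and name the Schwartz version and the MDRD form. Carrying the baseline equation forward is feasible: 3.C.2 measures height at follow-up in participants under 21, and anyone entering below 18 is still under 21 at month 36. Reconcile the ESRD wording across 3.E.1(c), 3.E.2(9) and the end of 3.E.1.b.(b), so that one definition applies or the two are named as different outcomes.

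As a secondary suggestion, count the 25 mL/min fall only when the next available study or local creatinine confirms it.

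The cost is limited to derivation rules, since local creatinine values are already collected. Confirmation would give slightly fewer events, and a fall at the last visit would need a later local value.

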The proposed design is a two-armed multicenter prospective cohort study with un-blinded standardized evaluation of pre-specified study outcomes in two defined separate and parallel cohorts of study participants. Sub-studies addressing specific research questions will be nested in the main cohorts. Pilot interventional clinical trials will also be performed on subsets of participants of the main cohorts. Up to two thousand participants will be enrolled into the NEPTUNE longitudinal cohorts over the enrollment period from the initial start date of December 11, 2009. The minimum follow-up period will be 36 months and subsequent annual in-person visits and/or chart abstraction for laboratories, vital and end-stage renal disease status may be conducted pending additional funding. The study will be comprised of two arms: Cohort A, a biopsy group composed of two main cohorts and Cohort B, a treatment-naïve, non-biopsy group of children less than 19 years of age. In the Cohort A (biopsy group), the two main cohorts will be specified by histopathologic criteria obtained from a baseline renal biopsy and pre-specified inclusion criteria. The first main cohort will be comprised of participants with histopathologic features consistent with Focal and Segmental Glomerulosclerosis (FSGS) or Minimal Change Disease (MCD) and the second histopathology cohort of Membranous Nephropathy (MN). Combined these Cohort A subsets are targeted to include a minimum of 300 participants to be enrolled under Protocol V4.1. These new enrollees will augment those enrolled under previous NEPTUNE protocol versions. Participants will be enrolled at academic clinical centers in the United States and Canada. The sampling frame is a consecutive series of all eligible and consenting patients undergoing diagnostic renal biopsy for any glomerular disease with the exception of renal disease due to systemic diseases such as lupus erythematosus (SLE), diabetes mellitus or multiple myeloma. A recruit-to-replace strategy will be utilized to ensure that a minimum sample size of 600 participants with FSGS, MCD and MN and 36 months of observation is preserved by the end of the recruitment period. After an initial pre-screening, participants will undergo a screening/eligibility visit, baseline visit, biopsy visit, and subsequently four month-interval follow-up visits during year one and thereafter, six month-interval follow-up visits after biopsy. Each participant will experience 9-10 study visits depending on date of enrollment and subsequent chart review and/or annual visits as funding and study timeline permits. Procedures to be performed during study visits include diagnostic baseline kidney biopsy, laboratory studies, blood and urine collection for biorepository, limited clinical examination, and administration of questionnaires. The primary study outcome of the two main biopsy cohorts are a change in urinary protein excretion and renal function. Several secondary outcomes will be evaluated including but not limited to composite of death, metabolic and hematologic complications, malignancies and infections. Descriptive and hypothesis-driven data analysis of the biopsy cohort studies will be performed at 30, 45 and 60 months of the study. For the FSGS/MCD cohort, a sample size of 250 participants is sufficient at two-sided alpha level of 0.05 to accurately predict the primary clinical outcome of Complete/Partial Remission vs. No Remission of urinary protein excretion (UPE) with a power of 75%-96%. For the MN cohort, a sample size of 200 participants is sufficient at two-sided alpha level of 0.05 to accurately predict the primary clinical outcome of Complete/Partial Remission vs. No Remission of urinary protein excretion (UPE) with a power of 70%-94%.

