- Clinical, serological or histological evidence of systemic lupus erythematosus (SLE) as defined by the ARA criteria. Patients with membranous in combination with SLE will be excluded because this entity is well defined within the International Society of Nephrology/Renal Pathology Society categories of lupus nephritis, and frequently overlaps with other classification categories of SLE nephritis (68)

- Clinical or histological evidence of other renal diseases (Alport, Nail Patella, Diabetic Nephropathy, monoclonal gammopathy (multiple myelomas), genito-urinary malformations with vesico-urethral reflux or renal dysplasia)
- Known systemic disease diagnosis at time of enrollment with life expectancy less than 6 months
- Unwillingness or inability to give a comprehensive informed consent
- Unwillingness to comply with study procedures and visit schedule
- Institutionalized individuals (e.g., prisoners)
- Laboratory information unavailable prior to consent and biopsy procedure subsequently supporting exclusion criteria will deem a participant ineligible

Consented individuals determined to be ineligible post-biopsy procedure will be requested to consent for their tissue and samples to remain part of the NEPTUNE biorepository. These samples may serve as non-nephrotic control samples for future studies and consenting participants will be compensated up to \$50 or as allowed by local IRBs.

3.B.7. Exclusion Criteria for Cohort B: cNEPTUNE

- End Stage Kidney Disease (ESKD) defined as the need for chronic dialysis or kidney transplant
- Prior solid organ or bone marrow transplant
- Secondary NS (systemic lupus erythematosus (SLE), vasculitis, Henoch Schonlein Purpura, Hepatitis B, C or HIV nephropathy)
- Clinical or histological evidence of other renal diseases (Alport syndrome, Nail Patella syndrome, Diabetic Nephropathy, monoclonal gammopathy (multiple myelomas), genito-urinary malformations with vesico-urethral reflux or renal dysplasia)
- Known systemic disease diagnosis at time of enrollment with life expectancy less than 6 months
- Unwillingness or inability to give a comprehensive informed consent
- Unwillingness to comply with study procedures and visit schedule
- Institutionalized individuals (e.g., prisoners)

3.B.8. Recruitment Targets

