Cystatin C has recently been proposed as a valuable marker of renal function and has been validated in large-scale epidemiological studies. Cystatins comprise a group of proteinase inhibitors, widely distributed in tissues and body fluids that form tight complexes with cysteine proteases. Cystatin C, a secreted molecule of this family, is increased in patients with malignant diseases, is related to insufficient renal function and appears to be a better marker of renal function than creatinine. Cystatins are secreted by many nucleated cells and the serum concentration is not as dependent on muscle bulk and nutritional state as serum creatinine. Serum concentrations of Cystatin C have been found to be potentially useful markers of renal function without most of the drawbacks of serum creatinine and the FDA has approved two assay techniques. Therefore, provisions will be made to set aside blood samples to measure serum Cystatin C concentrations as an additional measure of renal function if and when additional funds become available from ancillary proposals.

Justification for Choosing Renal Function as Primary Outcome Variable: We find it necessary to submit a defense for the use of the absolute reduction in GFR decline (time to event) rather than the rate of change (slope of GFR) as secondary renal function outcome in the FSGS/MCD and MN studies. Our rationales are straightforward. First, the absolute change in GFR is the more clinically important parameter. Secondly, the sample sizes of 250 and 200 participants, respectively, and duration of follow-up is not sufficient for a robust statistical power to estimate slope of GFR as an outcome. Thirdly, our experience in previous clinical studies causes us to be wary of the assumption of linear deterioration in renal function that underlies a slope-based analysis. This assumption is an empiric claim that has not always been substantiated. An estimated slope may be particularly erroneous when patients display a non-linear or otherwise erratic pattern of deterioration. In some cases, standard regression techniques may yield numerically large slopes that are not statistically different from zero. Missing measurements create instability in slope measurements. Also, slope evaluation techniques are poorly suited to censoring for dropouts and

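### Renal-function loss is ranked both primary and secondary, and end-stage renal disease is defined in conflicting ways that give different event lists

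*Protocol*

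**What the plan says.** **Rank.** The synopsis (1.B) states: "The primary study outcome of the two main biopsy cohorts are a change in urinary protein excretion and renal function". Section 3.E.1 opens with "The two primary outcome variables are" and lists renal function as the second of the two. The paragraphs closing 3.E.1.b are headed "Justification for Choosing Renal Function as Primary Outcome Variable". The text under that heading defends absolute GFR decline "as secondary renal function outcome in the FSGS/MCD and MN studies", and it goes on to call the three-part composite (ESRD, 50% decline, 25 ml/min/1.73m² decline) secondary as well. Section 3.F.4 reserves the word primary for the remission endpoint and places loss of renal function second.

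**ESRD.** There are three wordings:
- 3.E.1(2)(c): "End stage renal disease defined as estimated GFR ≤ 10 cc/min, initiation of maintenance dialysis or preemptive kidney transplantation".
- 3.E.1.b, justification: "time to ESRD (i.e. initiation of renal replacement therapy for usual clinical indications".
- 3.E.2(9): "Documented chronic dialysis or transplant shall be considered ESRD for the purposes of the NEPTUNE study, a final renal outcome".

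Only the first has an eGFR limb. Section 3.E.2(8) separately classes renal failure that needs renal replacement therapy for under 3 months as acute kidney injury.

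**Entry.** Cohort B excludes "End Stage Kidney Disease (ESKD) defined as the need for chronic dialysis or kidney transplant" (3.B.7). The Cohort A criteria (3.B.4 and 3.B.6) contain no ESKD, dialysis or minimum-eGFR item. The nearest is prior solid organ transplant.

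**The concern.** A primary outcome needs one rank and one event definition. Here an analyst who follows 3.E.1 and another who follows 3.E.2(9) would build different lists of ESRD events from the same records.

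The eGFR limb is also worded differently from its neighbours. Limbs (a) and (b) compare a follow-up value with baseline. Limb (c) mentions neither, and it requires no repeat value or duration. Section 3.C.1 lets renal-function values obtained for clinical care enter the study database, so values from an acute illness can be on file. Section 3.F.5.e plans Cox regression for the primary and secondary endpoints, and an event already present at entry has no meaningful event time there.

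At stake are which participants count as having reached end-stage disease, and whether the study reports renal-function loss as a primary or a secondary result.

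**Working it through.** The protocol gives no figure to reproduce on this point. The check compares the sections and then works out by hand where limb (c) matters.

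**1. Rank, by section**

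| Place | Rank of renal-function loss |
|---|---|
| 1.B | primary |
| 3.E.1 | primary, second of two |
| 3.E.1.b, heading of justification | primary |
| 3.E.1.b, text under that heading | secondary |
| 3.F.4 | second endpoint, after the primary endpoint of remission |

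The heading and the text beneath it cannot both stand.

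**2. Is it ESRD? The same patient under each definition**

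| Situation | 3.E.1(c) | 3.E.1.b | 3.E.2 |
|---|---|---|---|
| Chronic dialysis or preemptive transplant | yes | yes | yes |
| eGFR ≤ 10, sustained, no dialysis or transplant | yes | no | no |
| eGFR ≤ 10, transient, no renal replacement therapy | yes | no | no |
| eGFR ≤ 10, replacement therapy under 3 months, then recovery | yes | unclear: turns on whether temporary treatment counts as initiation | not under (9); acute kidney injury under (8) |

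**3. Where limb (c) adds events to the composite**

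Inputs, from 3.E.1: (a) a fall of 25; (b) a fall of 50%; (c) a value of 10 or less. Let B be baseline eGFR. I treat the three limbs as being on one scale, although (a) is stated per 1.73m² and (c) in cc/min.

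Thresholds: (a) is met at B − 25, (b) at B/2, (c) at 10.

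- B > 20: B/2 > 10, so (b) is met on the way down to 10. Equivalently, (B − 10)/B > 50%. Limb (c) adds nothing.
- B = 20: B/2 = 10, so (b) and (c) coincide.
- 10 < B < 20: 10 > B/2, so (c) is met before (b), and (a) cannot be met because B < 25.
 - B = 18 to 9.5: fall 8.5; 8.5/18 = 47.2%. Neither (a) nor (b) is met; (c) is.
 - B = 12 to 10: fall 2; 2/12 = 16.7%. Only (c) is met.
- B ≤ 10: (c) is met at entry, with no change at all.

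So within the composite the eGFR limb changes the event list only at baseline eGFR below 20.

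**4. ESRD taken alone**

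The other limbs no longer absorb the difference. A transient value of 10 or less without renal replacement therapy is an event under 3.E.1(c) at any baseline, and is not one under 3.E.1.b or 3.E.2(9).

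**5. Can limb (c) be met at entry?**

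Nothing in 3.B.4 or 3.B.6 prevents it for Cohort A. The protocol gives no baseline eGFR distribution, so neither the number with B ≤ 10 nor the number with B < 20 can be calculated.

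**The case against.** The strongest reply is that these are wording slips with limited effect. Sizing rests on classifying remission (1.B, 3.F.5), no stated alpha allocation turns on the rank of renal function, and 3.F.5.e applies Cox regression to primary and secondary endpoints alike. Outcome (2) is introduced as a change in renal function, so a state already present at entry is arguably no event. Removing prevalent cases from a risk set and requiring confirmation are ordinary SAP content, and 3.E.2 provides for possible event adjudication of a list that includes acute kidney injury and ESRD.

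Much of this stands, and it limits the size of the point. It does not remove it: the protocol itself fixes the definition more than once, in ways that a SAP cannot all follow, and adjudication needs one definition to apply.

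Four stronger readings are tempting, and the protocol does not support them:

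- A reader might infer that time to ESRD as argued for in 3.E.1.b is contaminated by recoverable kidney injury. That text bases it on renal replacement therapy, so a low eGFR without such therapy is not an event there. The problem arises only if limb (c) of 3.E.1 is applied.
- A reader might infer that the justification makes proteinuria remission the single primary outcome. It never says so, and 1.B and 3.E.1 state two. Correcting the word secondary would resolve the conflict just as well as demoting the outcome.
- A reader might infer that Cohort A participants do enter with eGFR of 10 or less. The criteria permit it; no figure shows that it happens.
- A reader might infer that removing limb (c) clears acute kidney injury from the composite. Limbs (a) and (b) carry no persistence rule either, so transient falls can still meet them.

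**Conclusion.** The point holds as an internal inconsistency that affects a stated primary outcome. Renal-function loss is primary in 1.B and 3.E.1, secondary in the text that justifies it as primary, and second in 3.F.4. ESRD has three wordings, and only that in 3.E.1(c) includes an eGFR value, with no reference to baseline or persistence.

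The effect on the composite is confined to participants with baseline eGFR below 20. For ESRD taken alone it extends to any baseline. The number of participants affected is unknown. The conclusion assumes that limb (c) is read literally and that the limbs share one eGFR scale. A SAP may add confirmation or risk-set rules; that could narrow the practical effect but would not make the protocol's sections agree.

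**What to change.** 1. Use one ESRD definition in 3.E.1(2)(c), 3.E.1.b and 3.E.2(9). The natural choice is the one already worded as study-wide in 3.E.2(9): documented chronic dialysis or transplant.
2. Exclude from the renal-function time-to-event analysis only participants who already meet that definition at baseline. Do not add an eGFR cut-off: once the eGFR limb is gone, someone at eGFR 9 and not on dialysis is still at risk of dialysis, transplant or a 50% decline.
3. If the eGFR limb is kept instead, require a new and sustained follow-up value, and carry the same definition into the other two places.
4. State one rank for the renal-function outcome by reconciling the 3.E.1.b justification with 1.B and 3.E.1, and align 3.F.4. This need not mean demotion. Enrollment began in December 2009, and 3.F.5.d already cites observed pediatric rates of kidney-function decline, so lowering a stated primary outcome now would be a data-aware change needing its own documented reason.

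The cost is protocol and event-definition wording, with no new data. There may be fewer ESRD events; the number cannot be estimated from the protocol. The change does not deal with transient falls that meet limbs (a) or (b).
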